Minors are not included due to the Mohs patient population of adults only who have undergone surgical excisions of skin cancers on the head or neck. Although participants are not required to be patients in the Mohs clinic, scars and healing may be significantly different in children, making the data less reliable and difficult to interpret. Any patient who has a condition that the PI assesses may put the subject at significant risk, may confound the study results, or may interfere significantly with the subject's participation in the study will be excluded from the study. Pregnant subjects are not included in the study due to insufficient data on the safety of lasers in pregnant patients.

Subject Discontinuation or Withdrawal from Study Participation

Subject Discontinuation

At any time within the trial, subjects may discontinue participation. Subjects who do not complete the trial will be asked to identify the reason for discontinuation and this information will be documented. If the date that they elect to discontinue from the trial occurs shortly after a treatment (within minutes to 30 days after treatment), patients will be asked to return for a follow-up 3 months to evaluate for any significant adverse events. No treatments will be performed. Only photographs of the scar and rating of the scar by the patient and evaluators will be performed at this visit. Also, collection of the diary will occur at this visit. If subjects discontinue from the trial after 30 days, patients will be followed up via phone for the reason of their discontinuation and asked to return the diary as soon as

possible. In either case, subjects will be given the contact information for the research office in case they have further concerns regarding their participation in the trial.

There are no guidelines or endpoints by which early decisions regarding efficacy or lack of efficacy will be made for this FDA approved device. However, the PI could stop the study early if significant unexpected adverse events occur, or enrollment and retention is not adequate.

Screen Failures

Subjects who do not meet the eligibility criteria will be considered screen failures. Any documentation completed prior to the determination of their status will be placed in one of the containers for shredding in our facility. The reason for the disqualification will be noted and the subject will be included in the count for screened subjects for publication purposes.

Study Device: CO2RE Laser

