A screening visit will occur whereby patients deemed appropriate for the study will have the segment of the scar with the most deformity defined for objective evaluation at each session. Baseline photographs of this area will be obtained and demographic data about the surgery that created the scar, associated wound healing complications, age of the scar, and the Fitzpatrick skin phototype will be collected. Randomization will occur at this visit and patients will receive their first treatment at this visit. Prior to treatment application, subjects will cleanse their face with a gentle cleanser, such as Cetaphil, provided in the office in order to remove all lotion, creams, make up, and sunscreen. An optional topical or local anesthetic medication will be offered to the subject and if desired by the subject will be applied to the treatment area approximately 20 minutes prior to the procedure. If the scar is deeper, an injection of numbing medicine (lidocaine with epinephrine) may be used as well. Once this time passes and the numbing medicine is working, the subject will be escorted to the procedure room. The treatment areas will be wiped clean of the numbing cream prior to the procedure. Just prior to the procedure, the subject's eyes will be covered with eye shields to protect their eyes. The treatment time may vary, but generally takes 10 minutes or less. During this time, subjects will hear the laser, which sounds like a bee buzzing, and will feel some warmth. Most patients report minimal discomfort during the procedure. There may be pinpoint bleeding, bruising, and crusting depending upon the area and extent of the treatment. After the treatment, patients will be provided with a 30-day diary to daily record treatment-related reactions: redness, swelling, pain, itching or color changes following treatment. If the subject has a history of recurrent fever blisters/cold sores on the lips or face, the subject will be offered a three day prescription for an antiviral medication that the subject can fill at the subject's pharmacy to prevent a recurrence since laser treatments may increase the chance of recurrent episodes. The subject would take one pill every twelve hours the day prior to treatment, on the treatment day, and the first day post-treatment. The subject or their insurance plan must cover the cost of the medication. This may delay the treatment to a later date within 30 days of the screening visit. If antibiotic/antiviral medications are needed, you and/or your insurance company will be responsible for covering this cost.

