the subject tends to form keloid scars or scars from minor trauma. Also, the subject should not participate in the study if the subject has taken oral isotretinoin medication within the past 6 months. In addition, the principle investigator may exclude the subject from the study if she determines that the study may put the subject at risk. The subject will provide written consent (permission) to be a participant in the study and for the research team to access the subject's health information to learn more about the surgery that resulted in the scar and the original features of the scar. Immediately before any study visit, the subject will be asked to not wear any make-up or use facial moisturizers (or moisturizers on the neck). The subject will be asked to cleanse their face with a gentle cleanser, such as Cetaphil, provided in the office prior to treatment.

Other procedures at this visit:

- The subject will have photographs taken of the scar that will be shared confidentially with two other research physicians in the study for them to answer questions about the scar.
- The subject will complete a questionnaire about the scar and another research physician will see the subject at this visit to evaluate the scar.

If the subject qualify for study treatment the following may occur at the same visit or at a return visit within 30 days. The following will occur:

- If the subject has a history of recurrent fever blisters/cold sores on the lips or face, The subject will be offered a three day prescription for an antiviral medication that the subject can fill at the subject's pharmacy to prevent a recurrence since laser treatments may increase the chance of recurrent episodes. The subject would take one pill every twelve hours the day prior to treatment, on the treatment day, and the first day post-treatment. The subject or their insurance plan must cover the cost of the medication. This may delay the treatment to a later date within 30 days of the screening visit.
- The subject will complete a pre-treatment questionnaire.
- The subject will receive laser treatment as randomized to either high energy or low energy treatment which includes:
 - Prior to treatment, the subject will be asked to cleanse his or her face with a gentle cleanser, such as Cetaphil, provided in the office in order to remove all lotion, creams, make up, and sunscreen.

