Patients who require evaluation outside of the three month windows +/- two weeks due to a related adverse event will be evaluated by the research team at the earliest convenience. If the nature of the evaluation is in regards to an adverse event/significant adverse event, a severe cutaneous reaction to the laser, or having an unrelated cosmetic procedure involving the study scar during the study, staff will evaluate the patient accordingly, document the event, and report any serious adverse events to the SLU IRB within a 24 hour window.

Completion of Study

At the completion of the study, the data obtained will be reviewed and analyzed with the aid of the Saint Louis University Center for Health Outcomes Research. This data will then be presented in the form of a paper and/or scientific poster. At the completion of the study, the data obtained will be presented in the form of a scientific paper and/or scientific poster.

Methods of Assigning Subjects to Treatment Arms

In terms of randomization, a spreadsheet will be created by the principle investigator with the aid of the research staff to predesignate the treatment assignment. For each patient that comes in, the principle investigator will use that as a guide to dictate the treatment arm assigned for that subject.

Blinding

Other than the investigating physician performing the laser treatment, no one (including the subjects, study coordinators, and the physicians who will be evaluating the response to treatment) will know who is receiving the high energy treatment or the low energy treatment until Visit #3.

Unblinding

At the Visit #3, subjects and the investigating physician performing the treatments will know the type of treatment that the subject in question received.

Concomitant Treatments

Prohibited

Patients will be prohibited from obtaining any additional cosmetic procedures during the study (i.e. dermabrasion, chemical peels) that may interfere with the interpretation of the results of the study.

Permitted

Patients will be permitted to continue using the moisturizers and cleansers that they have been using for the last 6 months. Patients will be allowed to take all oral medication (except isotretinoin) throughout the study.

Benefits and Alternatives

Benefits

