Access to all study materials will be kept in a locked facility within the SLU Dermatology Des Peres Office. Only staff members will have access to this room. With respect to the randomization spreadsheet, only the principle investigator will have access to this information. This information will be kept in a locked file cabinet in her office. The source documents created by the study site will be the primary forum for recording study data. When the study is completed, these documents will be placed in a long term storage facility owned by SLU.

Confidentiality

Interested subjects will sign a HIPPA form allowing access to relevant medical records. All study data will remain confidential, unless it is deemed by the principle investigator and/or research team members that it is important for the patient's health for study participation to be disclosed to appropriate parties (i.e. other medical providers). Study materials for each subject will have a deidentified code, such as subject Jane Doe is subject 001.

Data Protection

The master list, which will be password-protected, will be kept confidential to all research staff except the principle investigator. She will be the only unblinded individual in this study who will set the password for this document and will have access to the master list. Study materials for each subject will have a deidentified code, such as subject Jane Doe is subject 001.

Records Retention

Records will be retained within a locked office within the SLU Dermatology Des Peres Office

Posting to Clinical Trials Register and Publication

Information about this study will be posted to the Clinical Trials Register (accessible via http://www.clinicaltrials.gov). Recruitment for the study will be open until the study has obtained 50 patients. All recruitment information posted to the Clinical Trials Register will be reviewed and approved by the SLU IRB. Final data analysis and publication will be between July and August 2017.

References

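### Allocation is not concealed from the principal investigator, who makes and alone holds the assignment list and can exclude candidates at the visit where randomization occurs

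*Combined protocol and SAP*

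**What the plan says.** The relevant statements are spread over several sections of the combined protocol and SAP.

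- **Making the list.** Methods of Assigning Subjects to Treatment Arms: "a spreadsheet will be created by the principle investigator with the aid of the research staff to predesignate the treatment assignment". No method of generating the order is given.
- **Using the list.** Same section: for each arriving patient, "the principle investigator will use that as a guide to dictate the treatment arm assigned for that subject".
- **Access.** Direct Access, Data Handling and Record Keeping: "With respect to the randomization spreadsheet, only the principle investigator will have access to this information". Data Protection adds, of the principal investigator and the master list: "She will be the only unblinded individual in this study who will set the password for this document".
- **Discretionary exclusion.** Inclusion and Exclusion Criteria excludes: "Any patient who has a condition that the PI assesses may put the subject at significant risk, may confound the study results". Study Visit #1 repeats the discretion on grounds of risk: "the principle investigator may exclude the subject from the study if she determines that the study may put the subject at risk".
- **Timing.** Study Procedures, on the screening visit: "Randomization will occur at this visit and patients will receive their first treatment at this visit". Treatment may be postponed by up to 30 days.
- **Records of those not entered.** Screen Failures has the documents completed so far shredded. Only the reason is noted and the person counted.

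The Blinding section keeps subjects, coordinators and evaluating physicians unaware of the arm until Visit #3.

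**The concern.** A randomized comparison is protected at entry only if those who influence who enters cannot know which arm the next entrant will get. Here one person holds both the list and a broad, judgement-based ground for exclusion. If she knows that the next slot is high energy, she may, consciously or not, view a poor-prognosis scar as unsuitable; if the next slot is low energy, the same scar may be let in. The arms would then differ at baseline in ways related to outcome. Blinding subjects and raters protects assessment after assignment and does nothing about this. The Data Analysis section describes no baseline adjustment, and analysis could not reliably repair such a bias in any case.

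**Working it through.** The question is structural, and the plan gives no figure to reproduce. The check is whether any step separates knowledge of the next assignment from the decision on entry.

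1. **Who knows the next arm before entry is settled?** The principal investigator. She creates the list in advance, alone may consult it, and assigns from it.
2. **Who can stop a candidate entering?** The principal investigator, under both Inclusion and Exclusion Criteria and Study Visit #1.
3. **When do the two meet?** At the screening visit, where randomization also occurs.
4. **Does anything intervene?** The documents describe no sealed envelopes, no central or third-party release, and no rule that eligibility be recorded before the list is consulted. Study Procedures does mention suitability and the scar segment first: "patients deemed appropriate for the study will have the segment of the scar with the most deformity defined for objective evaluation". That order conceals nothing, because the list already exists and is in the investigator's hands.
5. **Extent.** The study population is 50, and every assignment is designated beforehand. Knowable in advance to the list holder: 50 of 50.
6. **Who else may have seen the list?** Research staff help to make it. That has to be reconciled with investigator-only access and with blinded coordinators.
7. **Does the investigator also treat?** No sentence says so outright. But Blinding says that only the treating physician knows the arm before Visit #3, and Data Protection names the principal investigator as the only unblinded person. Read together, these suggest that she treats, and so would see every past assignment even if the list were taken from her. This bears on the remedy; the finding does not need it.

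**Illustration only.** The following shows how a bias of this kind would act. Every input except the total of 50 is assumed: 25 per arm, no true effect, a two-sided two-sample t-test, correlation ρ between the investigator's view of prognosis and outcome, and a share x of candidates passed over (least favourable for high-energy slots, most favourable for low-energy slots).

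- Shift in SD = 2ρφ(z)/(1 − x), where z is the normal quantile cutting off x. Type I error comes from the noncentral t with 48 df and noncentrality shift × √(25/2).
- x = 0.10, ρ = 0.5: 2 × 0.5 × 0.1755/0.90 = 0.195 SD. Noncentrality is 0.195 × 3.536 = 0.69, and type I error is 10.4% instead of 5%. Candidates passed over to enrol 50: 50 × 0.10/0.90 = 5.6.
- If only one arm's slots are affected, the shift halves to 0.098 SD and type I error is 6.3%.
- Over x = 5–20% and ρ = 0.3–0.7, type I error runs from 5.6% to 39.7% with selection in both directions, and from 5.1% to 13.6% in one direction. Allowing for the narrower within-arm SD after selection moves the two-direction figures to 5.6–47.7%, with 10.8% in the middle case.

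The width of these ranges reflects how little the documents fix. The Data Analysis section names a chi-square test and a Wilcoxon signed rank test between study visits, and no two-arm t-test. The finding does not rest on these figures.

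**The case against.** The best defence has four parts.

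- **Subjects and raters are blinded, and a treating physician must know the arm.** Both are true. But knowing the arm at treatment is compatible with not knowing it at enrolment, and blinding does not reach the entry decision.
- **Screening leaves a trace.** Each disqualification has its reason noted and is counted, so a large volume of discretionary exclusions would be visible. This stands: the upper illustrative figures need about 12.5 of 62.5 candidates to be passed over, and they should not be used to argue severity. A handful of exclusions would not stand out, and a reason plus a count does not show which slot was pending.
- **The list is meant to be followed.** A reader might infer from the guide wording in Methods of Assigning Subjects that the investigator is free to depart from the list. The documents do not support that. The same section speaks of predesignating and dictating the arm, and Study Visits #1 and #2 refer to treatment as randomized. One loose phrase calls for a clarification of wording; it does not establish a non-binding list. Concealment fails even if the list is followed exactly.
- **No selection is shown.** A reader might also infer that the order is not random, or that the investigator will look ahead. Neither follows: the trial is described as randomized, the generation method is simply not stated, and no intention to select appears anywhere. The flaw is that nothing prevents it.

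**Conclusion.** The concern holds. Following the plan as written leaves allocation unconcealed from a person with power over entry, for all 50 assignments, and no other section cures this. It should be corrected before enrolment, because bias at entry cannot be reliably removed afterwards.

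The conclusion rests on the stated division of tasks, with no numerical assumption. The size of any bias cannot be estimated from the documents. A claim that the false-positive rate is inflated to a particular level would go beyond them, since it needs an unnamed test and assumed selection behaviour. That the investigator also treats is a reasonable inference from two sections, and no sentence states it.

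**What to change.** 1. **Independent list.** Someone independent of enrolment and treatment generates the random list; the Center for Health Outcomes Research, already engaged for analysis, is one option. Stratify by scar age (8–51 weeks; 52 weeks or older) with randomly varied, undisclosed block sizes. State that neither the investigator nor research staff see the list in advance, and amend the assignment, access and data-protection text to match.
2. **Sealed release.** Use sequentially numbered, opaque, sealed envelopes, one set per stratum. Before an envelope is opened, record, sign and date eligibility, any discretionary exclusion by the investigator with its reason, the scored scar segment and the baseline assessments. The blinded research physician already present at Visit 1 records the segment and baseline ratings. Only the treating physician opens the envelope, so subjects, coordinators and raters stay blinded.
3. **Wording.** Replace the guide phrase with a statement that the released assignment is followed, and that any departure, or any exclusion after release (including during a postponement of first treatment), is logged as a protocol deviation.
4. **Screening log.** Keep a de-identified sequential log (number, date, scar-age group, reason) in place of a reason and a count alone.

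**Cost.** One amendment covering Screen Failures, Study Procedures, Study Visit #1, the assignment section, Data Analysis (the Center's added role), and the record-keeping and data-protection sections; two sets of envelopes; a short log; a small task for the Center. No extra subjects or visits.

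**Residual downside.** A treating physician who sees past assignments can sometimes guess the next one near a block end. With fixed blocks of 4, the best guess would be right (1/2 + 2/3 + 2/3 + 1)/4 = 70.8% of the time, against 100% for the list holder now. Varied block sizes, and recording exclusions before release, limit this without removing it.

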The primary objective is to assess the efficacy of fractionated carbon dioxide laser in improving surgical scars. Objective assessment of the scars will involve the Vectra microtopographic imaging system to measure changes in the length of the scar. The Patient and Observer Scar Assessment Scale (POSAS) is a validated survey that will be utilized for subjective assessments of the vascularity, pigmentation, thickness, pliability, surface area, relief, pain, and pruritus.

The secondary objective will be to evaluate the tolerability of the laser, by assessing the severity and duration of known side effects of laser therapy such as erythema, edema, burning sensation, post-inflammatory pigment changes, infection, scarring, xerosis, pruritus, bronzing, and any other adverse events that arise following treatment. Patients will be given a 30-diary after each treatment to document this information.

Selection and Withdrawal of Study Subjects

Study Population

The study population will consist of 50 adult patients 18 years of age or older with surgical scars located on the head and neck.

Minors are not included due to the Mohs patient population being adults only who have undergone surgical excisions of skin cancers on the head or neck. Although participants are not

required to be patients in the Mohs clinic, scars and healing may be significantly different in children, making the data less reliable and difficult to interpret.

Inclusion and Exclusion Criteria

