For the inclusion criteria, adult patients of all Fitzpatrick phototypes who have surgical scars of the head and neck will be screened for this study. There is no data to suggest that there is a difference in the appearance of older (more than 1 year old from the initial injury) and newer scars (at least 8 weeks after surgery) post-therapy. Most scars are fully mature at exactly 1 year from the date of the initial injury, so in the "older scar" cohort one may presume (in the absence of any confirmed findings in the medical literature) that any changes to these scars post-therapy will be an effect from the laser. The minimum age of the scar will be eight weeks from the initial surgery, as the scar has healed enough to determine if additional fine tuning may be helpful. In addition, standard practice is to allow a scar to heal for 8 weeks before laser treatment. Therefore subjects may be enrolled in the younger scar group if the scar is 8 weeks – 51 weeks from occurrence, and enrolled in the older scar group if the scar is 52 weeks or older from time of occurrence. We will aim to recruit 20 patients with old scars (10 of which will be in the high energy treatment group, and 10 of which will be in the low energy treatment group). In terms of statistical analysis, we will review whether there is a difference between the post-treatment measurements and appearance of older scars and newer scars. Patients must be able to understand the informed consent, willing to come to the office for treatments and capable of following post-treatment instructions.

In terms of exclusion criteria, patients who have had prior laser treatments to the face and neck, have a history of keloid formation, scars resulting from non-surgical etiologies (i.e. minor trauma), isotretinoin use in the last 6 months prior to study enrollment, and allergy to topical lidocaine will not be eligible for the study.

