As soon as the PI becomes aware of an AE that meets the criteria for an SAE, the SAE should be documented to the extent that information is available. A report must be submitted by the study site to the SLU IRB, within 24 hours. Forms for reporting SAEs will be provided to the study site. SAEs will be recorded from the time of informed consent, through the end of the study. If in the opinion of the Investigator, an SAE occurring outside the specified time window (i.e., following subject completion or withdrawal from the study), is deemed to be device related, then the event should be reported with 24 hours as outlined above. The Investigator should institute any clinically necessary supplementary investigation of SAE information.

Death

In the case of subject death, any post-mortem findings/reports will be requested and a report (even if a preliminary diagnosis/cause of death is available) will be submitted to the SLU IRB within 24 hours of learning about the death.

Reporting of Pregnancy

In the case of subject pregnancy, the subjects will be discontinued from the study and will be followed leading up to delivery.

Data Analysis and Statistical Considerations

At the completion of the study, the data obtained will be reviewed and analyzed with the aid of the Saint Louis University Center for Health Outcomes Research. A chi-square test along with the Wilcoxon signed rank test will be performed to assess significant difference between clinical improvement scores between study visits. There is no data to suggest that there is a difference in the appearance of older (more than 1 year old from the initial injury) and newer scars post-therapy. We will aim to recruit 20 patients with old scars (10 of which will be in the high energy treatment group, and 10 of which will be in the low energy treatment group). In terms of statistical analysis, we will review whether there is a difference between the post-treatment measurements and appearance of older scars and newer scars.

Quality Control and Quality Assurance

Quality control and assurance for this study will be performed by an internal review every 3 months to ensure that the data collected is in accordance with the goals of this study and to address any issues with data collection or performance of any study procedures.

Direct Access, Data Handling and Record Keeping

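### The plan aims for 20 older scars split 10 and 10 between the arms, but describes no stratification, quota or adjustment by scar age that would deliver or protect that split

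*Combined protocol and SAP*

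**What the plan says.** Inclusion and Exclusion Criteria defines a younger group (8 to 51 weeks) and an older group; a patient is "enrolled in the older scar group if the scar is 52 weeks or older from time of occurrence". It then sets the target: "We will aim to recruit 20 patients with old scars". These are to be divided equally, 10 to each energy arm. Data Analysis and Statistical Considerations repeats the target and adds that older and newer scars will be compared after treatment. The tests named there are a chi-square test and a Wilcoxon signed rank test between visits. Neither carries a scar-age term.

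Methods of Assigning Subjects to Treatment Arms gives the whole allocation procedure in two sentences. The first is that "a spreadsheet will be created by the principle investigator with the aid of the research staff to predesignate the treatment assignment". The second is: "For each patient that comes in, the principle investigator will use that as a guide to dictate the treatment arm assigned for that subject". Strata, separate lists, blocks and an allocation ratio are not mentioned.

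Study Population gives the total as 50. Posting to Clinical Trials Register and Publication says: "Recruitment for the study will be open until the study has obtained 50 patients". Neither section sets a minimum or maximum by scar age.

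**The concern.** The target has two parts, a number of older scars and a split between arms, and each needs a mechanism. The split needs allocation within scar-age group. The number needs some control on who fills the 50 places. The plan describes neither.

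Scar age is more than an ordinary baseline covariate here. Inclusion and Exclusion Criteria notes that most scars are mature at one year, and presumes that change in the older cohort can therefore be credited to the laser. It follows that change in newer scars may be partly natural maturation. Both arms receive active laser and there is no untreated group. If one arm happens to hold more newer scars, some of the observed difference between energy levels could be maturation, and the planned analysis has no term to separate the two. The older-scar subset, which is the cleaner one on the protocol's reasoning, could also turn out small or uneven.

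**Working it through.** **Inputs from the documents.** Total 50; older-scar target 20, split 10/10; cut at 52 weeks; one described spreadsheet; no scar-age quota.

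**Assumptions, not in the documents.** Allocation 1:1; a list that ignores scar age; and, for step 4 only, the share p of older scars among those enrolled.

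**Step 1. Can the plan's own figures be reproduced?** No. The documents give no significance level, power, effect size or standard deviation, so neither 50 nor 20 (10/10) can be derived. The check is instead how often the described method would give the stated split.

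**Step 2. Split of 20 older scars.** Let k be the number in the high-energy arm.

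- Simple randomisation: P(k) = C(20,k)/2^20. For k = 10: 184,756/1,048,576 = 17.6%.
- Arms fixed at 25/25: P(k) = C(25,k)·C(25,20−k)/C(50,20). For k = 10: 22.7%.
- A single list in blocks of 4, by simulation (100,000 runs): 22.5% for k = 10.

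| Split | Simple 1:1 | Fixed 25/25 | Single list, blocks of 4 |
|---|---|---|---|
| exactly 10/10 | 17.6% | 22.7% | 22.5% |
| 12/8 or worse | 50.3% | 38.7% | 39.1% |
| 13/7 or worse | 26.3% | 14.8% | not run |

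**Step 3. What an uneven split means.** With 25 per arm, 12/8 is 48% versus 32% older scars, and 13/7 is 52% versus 28%. If newer scars improved by an extra δ through maturation alone, and this simply added to any laser effect, the unadjusted arm difference would shift by (0.48 − 0.32)δ = 0.16δ or (0.52 − 0.28)δ = 0.24δ. The documents give no value for δ, so the shift cannot be put in scale points.

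Loss of precision is small. Within the older scars, 13/7 instead of 10/10 multiplies the standard error of an arm difference by √[(1/13 + 1/7)/(1/10 + 1/10)] = √(0.2198/0.2) = 1.05.

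**Step 4. Number of older scars.** If patients are taken as they come until 50 are enrolled, the number of older scars is Binomial(50, p).

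| p | P(fewer than 20 older) |
|---|---|
| 20% | 99.9% |
| 30% | 92% |
| 40% | 45% |
| 50% | 6% |
| 60% | 0.1% |

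**Step 5. With separate lists.** In blocks of 4, 20 older scars fill five complete blocks, so the split is exactly 10/10. Thirty newer scars fill seven blocks (14/14) plus two places of an eighth, so the split is 15/15 or, at worst, 14/16.

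**The case against.** A reader might infer that the list is known to be unstratified, and that the plan therefore contradicts itself. The documents do not go that far. They are silent on strata, and a spreadsheet with a section for each scar-age group would fit everything they say. The supportable statement is that no stratification is described.

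A reader might also infer that the high-versus-low comparison is biased. It is not shown to be. Chance imbalance under genuine randomisation adds variance, not bias in expectation. The maturation argument is expressly a presumption made without confirmed findings, and the same section says no data suggest that older and newer scars look different after therapy. That is absence of data rather than evidence of equivalence, but it does mean no effect of scar age is established.

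Three further points stand. The 20 is worded as an aim, not a quota. The recruitment sentence sits in the registry-posting section and says when recruitment ends; it does not rule out actively seeking older scars, so the figures in step 4 hold only for passive enrolment. And counting 11/9 as a miss is strict: with arms of 25/25 the split is 11/9 or closer 61% of the time (100 − 38.7) and 12/8 or closer 85% (100 − 14.8).

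What survives is that the plan names both a factor and a split, repeats them in the statistics section, rests a planned comparison on them, and gives no means of reaching them. If the 10/10 were instead reached by departing from the list case by case, assignment would no longer be random. The documents do not say this will happen, but a list that serves only as guidance leaves room for it.

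**Conclusion.** The point holds as a gap between a stated aim and the procedures described, and should be corrected. Under 1:1 allocation with a list that ignores scar age, the intended split among 20 older scars occurs about 18–23% of the time, and a split of 13/7 or worse about 15–26% of the time. Whether 20 older scars are reached at all depends on a share that the documents do not give.

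The consequence is a risk of chance imbalance in a factor the protocol itself uses, with hedging, to attribute change to the laser, in a trial of 50 with no planned adjustment. It does not invalidate the trial, and the cost in precision is modest.

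**What to change.** In Methods of Assigning Subjects to Treatment Arms, specify two 1:1 permuted-block lists generated in advance, one for scars of 8–51 weeks and one for scars of 52 weeks or more, for example in blocks of 4. State that the lists are followed strictly in order, rather than used as guidance.

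In Data Analysis and Statistical Considerations, include the scar-age stratum in the high-versus-low comparison. The tests now named are described only as between visits, so that comparison has to be written down first.

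For the number, choose one of two courses: reserve 20 of the 50 places for older scars, so that newer-scar entry closes at 30; or say plainly that 20 is a target that may not be reached.

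The lists cost almost nothing, because Study Procedures already has age of the scar collected at the visit where randomisation takes place. Reserving places may slow recruitment. That matters because Early Study Termination lets the investigator stop for inadequate enrolment. If the spreadsheet is already organised by scar age, one sentence saying so would settle the allocation part.
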